14.2 Operational Definition and Reporting Adverse Events/Reactions

Information about adverse events/reactions whether volunteered by the participant, discovered by investigator questioning or detected through physical examination, laboratory test or other investigation will be collected and recorded on the relevant CRF.

Adverse events /reactions will be collected for all participants from the time of registration into the trial until 30 days post-operatively and will be evaluated for duration and intensity according to the National Cancer Institute Common Terminology Criteria for Adverse Events V4.0 (NCI-CTCAE). A copy is provided in the Investigator Site File and may be obtained at:

http://evs.nci.nih.gov/ftp1/CTCAE/About.html

CTCAE_4.03_2010-06-14_QuickReference_8.5x11.pdf

Published date: 28 May 2009.

14.3 Operational Definition and Reporting SAEs/SARs and SUSARs

All SAEs, SARs and SUSARs occurring from the time of registration until 30 days post-operatively must be recorded on the relevant form and faxed to the CTRU within 24 hours of the research staff becoming aware of the event. Once all resulting queries have been resolved, the original form should also be posted to the Research Fellow at SJUH and a copy to be retained on site.

For each SAE, SAR, and SUSAR the following information will be collected:

- full details in medical terms and case description
- event duration (start and end dates, if applicable)
- action taken
- outcome
- seriousness criteria
- causality (i.e. relatedness to trial drug / investigation), in the opinion of the investigator)*
- whether the event would be considered expected or unexpected .

*Assessment of causality and preliminary expectedness must be made by a doctor. If a doctor is unavailable, initial reports without causality and expectedness assessment should be submitted to CTRU within 24 hours, but must be followed up by medical assessment as soon as possible thereafter.

Any change of condition or other follow-up information should be faxed to the CTRU as soon as it is available or at least within 24 hours of the information becoming available. Events will be followed up until the event has resolved or a final outcome has been reached.

All SAEs assigned as both suspected to be related to IMP-treatment and unexpected will be classified as SUSARs and will be subject to expedited reporting to the Medicines and Healthcare products Regulatory Authority (MHRA) and Irish Medicines Board (IMB). The CTRU will inform the MHRA, IMB the main REC and the Sponsor of SUSARs within the required expedited reporting timescales.

Please ensure that each event is reported separately and not combined on one SAE form.

Events not classed as SAEs

The following events will not be recorded as SAEs within this trial:

Hospitalisation for:

- Routine treatment or monitoring of the studied indication not associated with any deterioration in condition.
- Treatment that was elective or pre-planned, for a pre-existing condition not associated with any deterioration in condition.
- Admission to hospital or other institution for general care not associated with any deterioration in condition.

- Treatment on an emergency, outpatient basis for an event not fulfilling any of the definitions for serious as given above and not resulting in hospital admission.
- Disease progression

Expected AEs

The following events **will be** classed as expected surgical AEs. Any such events meeting the seriousness criteria should be reported as SAEs but will not be reportable as SUSARs unless the Investigator considers the severity to be unexpected:

Operative

- Damage to organ/structure e.g.
 - o Bowel
 - o Bladder/ureter
 - o Major vessel
 - o Nerves
- Faecal contamination
- Haemorrhage
- Surgical emphysema
- Failure of surgical equipment (laparoscopic equipment)

Post-operative

- Altered bowel habit
- Anastomotic leak
- Gastrointestinal fistula
- Gastrointestinal ischaemia/necrosis
- Gastrointestinal obstruction
- Gastrointestinal perforation

- Gastrointestinal stricture/stenosis
- Gastrointestinal ulceration
- Haemorrhage
- Hernia
- Ileus
- Intra-abdominal/pelvic abscess
- Post-operative peritonitis
- Sexual dysfunction
- Stoma prolapse/necrosis
- Urinary dysfunction
- Urinary retention
- Wound infection
- Wound dehiscence

Cardiorespiratory

(May be operative or post-operative)

- Respiratory, including
 - o Acute respiratory distress syndrome/respiratory failure
 - o Aspiration
 - o Atelectasis
 - o Bronchospasm
 - Pleural effusion
 - o Pneumonia/chest infection
 - Pulmonary embolus (or DVT)
- Cardiac, including
 - o Arrhythmia
 - Cardiac failure
 - o Ischaemic heart disease/ myocardial infarction
- Cardio-respiratory arrest

Other

- Acute renal failure
- Back pain
- Cerebrovascular attack/stroke
- Disseminated intravascular coagulation
- Distal limb ischaemia/compartment syndrome
- Metabolic acidosis
- Necrotising fasciitis
- Pressure sore
- Pseudomembranous colitis
- Scrotal swelling
- Sepsis
- Subcutaneous emphysema
- Urinary tract infection
- Delerium

Fax Number for reporting SAE/SARs and SUSARs: [name]

14.4 **Pregnancies and Suspected Pregnancies**

If a participant becomes pregnant while enrolled in this clinical trial or up to three months following administration of 5-ALA the investigator or designated site personnel must notify the CTRU within 24 hours of learning of the pregnancy. The Sponsor will be responsible for notifying SJUH Research Fellow. Pregnancy is a contraindication to administration of 5-ALA. Participants, spouses, or partners will be followed through the outcome of the pregnancy. The Investigator will be required to report the results to the Sponsor.

If the outcome of the pregnancy meets a criterion for immediate classification as an SAE - spontaneous abortion (any congenital anomaly detected in an aborted foetus is to be documented), stillbirth, neonatal death, or congenital anomaly—the Investigator should repeat the procedures for expedited reporting of SAEs as outlined above.

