12.1 Investigational Medicinal Products

The following are classified as Investigational Medicinal Products (IMPs).

• 5-ALA

5-ALA (in the form of its hydrochloride, 5-ALA HCI) has been used in humans for fluorescence diagnosis and photodynamic therapy in a variety of cancers. It preferentially accumulates in cancer cells where it is metabolised to Protoporphyrin IX (PpIX), a component of the Heme pathway and an endogenous photosensitiser (22).

5-ALA is safe for human administration; it is used topically in dermatological malignancies, intravesically to detect bladder cancers, and orally in premalignant oesophageal lesions and malignant gliomas (23). It has also been administered intradermally, intraperitoneally and intravenously in experimental studies without adverse effects. 5-ALA is available in various forms depending on the intended mode of application. When administered orally in high doses for photodynamic therapy, side-effects may include nausea, tachycardia, hypotension, photosensitivity, and a transient rise in aspartate transaminase and bilirubin When 5-ALA is administered orally in conjunction with surgical resection of malignant brain tumours side effects can include brain oedema. 5-ALA is cleared by the liver and kidneys with a short half-life and return to baseline levels by 24 hours. Much smaller doses are required for fluorescence diagnosis; typically 20 mg/kg.

Please refer to the Pharmacy and IMP Trial Site Operating Procedure for full details of the trial IMP management requirements, including details of IMP labelling,

destruction, accountability and disposal records.

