14.1 General Definitions

Adverse Events (AE)

Any untoward medical occurrence in a patient or clinical trial subject administered a medicinal product and which does not necessarily have a causal relationship with this treatment.

Adverse Reactions (AR)

All untoward and unintended responses to an investigational medicinal product related to any dose administered. This definition implies a reasonable possibility of a causal relationship which is supported by facts, evidence or arguments to suggest a causal relationship. This definition includes medication errors and uses outside what is foreseen in the protocol (i.e. if an AR occurs as a result of a medication error).

Serious Adverse Events (SAE)

Any untoward medical occurrence or effect that:

- results in death,

- is life-threatening
- requires hospitalisation or prolongation of existing hospitalisation,
- results in persistent or significant disability or incapacity,
- is a congenital anomaly or birth defect,
- jeopardised the subject or required intervention to prevent one of the above.
- -is otherwise considered medically significant by the Investigator.

Medical and scientific judgement must be exercised in deciding whether an event is serious (see protocol section 14.5 for Responsibilities). These characteristics / consequences must be considered at the time of the event and do not refer to an event which hypothetically may have caused one of the above.

Where an SAE is deemed to have been related to an IMP used within the trial the event is termed as a **Serious Adverse Reaction (SAR)**.

Suspected Unexpected Serious Adverse Reactions (SUSAR)

An adverse reaction, the nature and severity of which is not consistent with the applicable product information in the summary of product characteristics. Severity describes the intensity of the event.

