14.5 Responsibilities

Principal Investigator (PI):

- 1 Checking for AEs and ARs when participants attend for treatment / follow-up.
- 2 Using medical judgement in assigning seriousness, causality and preliminary expectedness using the Reference Safety Information approved for the trial.
- 3 Ensuring that all SAEs and SARs (including SUSARs) are recorded and reported to the CTRU within 24 hours of becoming aware of the event and provide further follow-up information as soon as available.
- 4 Ensuring that SAEs and SARs (including SUSARs) are chased with CTRU if a record of receipt is not received within 2 working days of initial reporting.

5 Ensuring that AEs and ARs are recorded and reported to the CTRU in line with the requirements of the protocol.

CTRU

- 1 Provide office hours cover for receipt of all initial and follow up SAEs, SARs, and SUSARs. The CTRU will conduct an initial review of the core dataset prior to forwarding to CI/Research Fellow for medical review.
- 2 Expedited reporting of SUSARs to the relevant Competent Authorities (MHRA and Irish Medicines Board [IMB]), Main RECs in UK and Ireland and Sponsor within required timelines.
- 3 Pass all data to the Research Fellow for databasing.

SJUH Research Fellow:

- 1 Central data collection and verification of AEs, ARs, SAEs, SARs and SUSARs according to the trial protocol onto a database.
- 2 Preparing annual progress reports to Main RECs in UK and Ireland and periodic safety reports to TSC and DMEC as appropriate.
- 3 Reporting safety information to the independent oversight committees identified for the trial (Data Monitoring & Ethics Committee (DMEC) and / or Trial Steering Committee (TSC)) according to the Trial Monitoring Plan.
- 4 Preparing standard tables and other relevant information for the DSUR in collaboration with the CI and ensuring timely submission to the MHRA, IMB and Main REC in UK and Ireland.
- 5 Notifying Investigators of SUSARs that occur within the trial.
- 6 Checking for (annually) and notifying PIs of updates to the Reference Safety Information for the trial.
- 7 Reporting safety information to the CI, delegate or independent clinical reviewer for the ongoing assessment of the risk / benefit according to the Trial Monitoring

Plan.

- 8 Reporting events to collaborating pharmaceutical company in accordance with the trial contract.
- 9 Any duties as delegated by the CI

Chief Investigator (CI) / delegate or independent clinical reviewer:

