- 1 Clinical oversight of the safety of patients participating in the trial, including an ongoing review of the risk / benefit.
- 2 Using medical judgement in assigning seriousness, causality and expectedness of SAEs where it has not been possible to obtain local medical assessment.
- 3 Immediate review and determination of expectedness for all events assessed as related to the IMP in the opinion of the local investigator.
- 4 Review of specific SAEs and SARs in accordance with the trial risk assessment and protocol as detailed in the Trial Monitoring Plan.
- 5 Assigning Medical Dictionary for Regulatory Activities (MedDRA) or Body System coding to all SAEs and SARs.
- 6 Preparing the clinical sections and final sign off of the Development Safety Update Report (DSUR).

Trial Steering Committee (TSC):

In accordance with the Trial Terms of Reference for the TSC, periodically reviewing safety data and liaising with the DMEC regarding safety issues.

Data Monitoring & Ethics Committee (DMEC):

In accordance with the Trial Terms of Reference for the DMEC, periodically reviewing unblinded overall safety data to determine patterns and trends of events, or to identify safety issues, which would not be apparent on an individual case basis.

Pharmaceutical company:

- 1 Supply of the Study Drug according to the Drug Transfer Agreement
- 2 Labelling of the Study Drug which with the label provided by the sponsor
- 3 Information of the Principal Investigator on all important new safety information for the Study Drug without delay.
- 4 Information of the Principal Investigator on relevant Quality defects as soon as they are known.

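### The expected-event list in section 14.3 removes SUSAR status without a causality limit, in conflict with the product-based test of expectedness in sections 14.1, 14.3 and 14.5

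*Protocol*

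**What the plan says.** Four rules in the protocol bear on when a serious event becomes a SUSAR.

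- Section 14.1 defines a SUSAR as "An adverse reaction, the nature and severity of which is not consistent with the applicable product information in the summary of product characteristics". The yardstick is the product, and both nature and severity count.
- Section 14.3 gives the operational rule: "All SAEs assigned as both suspected to be related to IMP-treatment and unexpected will be classified as SUSARs". These go by expedited report to the MHRA, the IMB, the main REC and the Sponsor.
- Section 14.3, under the expected AEs, gives a list of events that are to be "classed as expected surgical AEs". Those that meet a seriousness criterion "should be reported as SAEs but will not be reportable as SUSARs unless the Investigator considers the severity to be unexpected".
- Section 14.5 describes the Principal Investigator's duty as "Using medical judgement in assigning seriousness, causality and preliminary expectedness using the Reference Safety Information approved for the trial". It also gives the Chief Investigator, or a delegate or independent clinical reviewer, a second step: "Immediate review and determination of expectedness for all events assessed as related to the IMP in the opinion of the local investigator".

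**The concern.** The list answers a different question from the one a SUSAR assessment asks. It says what is expected after a colectomy. Sections 14.1 and 14.5 ask what is expected of 5-ALA. A complication can be ordinary for the operation and still be unknown for the drug.

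The two can coincide here. Section 11.1.2 has 5-ALA given 4 to 6 hours before the operation, so a drug reaction and a perioperative complication can fall in the same period. An investigator may suspect 5-ALA, find the event on the list, regard its severity as usual for surgery, and conclude that no SUSAR arises. Under 14.1 the same event could be one. At stake are the expedited external report and the notice to the other investigators.

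**Working it through.** No sample size, error rate or event rate enters this point, and the plan gives no figure to reproduce. The check compares the rules and counts the list.

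**1. When the exemption has an effect.** Under the operational rule in 14.3, a SUSAR must be serious, suspected to be related to 5-ALA, and unexpected. Take a serious event that is on the list and whose severity the Investigator does not consider unexpected.

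| Suspected related to 5-ALA? | Covered by the product information? | Under 14.1, the 14.3 rule and 14.5 | Under the 14.3 list |
|---|---|---|---|
| No | Either | Not a SUSAR | Not a SUSAR |
| Yes | Yes | Not a SUSAR | Not a SUSAR |
| Yes | No | SUSAR | Not a SUSAR |

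The list changes the result only in the last row. In the other two it adds nothing.

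**2. What the clause drops.** The 14.1 test turns on "the nature and severity of which is not consistent with the applicable product information in the summary of product characteristics". The list settles the nature of the event in advance, by reference to surgery. Only severity is left open, and the clause refers to neither the product information nor the Reference Safety Information.

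**3. Size of the list.** There are 5 operative, 19 post-operative, 11 cardiorespiratory and 14 other entries: 5 + 19 + 11 + 14 = 49. Splitting organ damage into its four examples gives 49 − 1 + 4 = 52. Haemorrhage appears twice.

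**4. Overlap with the drug effects that the protocol names.** Section 12.1 says that after high oral doses "side-effects may include nausea, tachycardia, hypotension, photosensitivity, and a transient rise in aspartate transaminase and bilirubin", and adds brain oedema in brain tumour surgery. Section 6.5 adds vomiting. Only tachycardia plausibly overlaps with a list entry (arrhythmia). Acute renal failure, stroke and disseminated intravascular coagulation are on the list and are not among the named 5-ALA effects. If the Reference Safety Information does not cover them either, they fall in the last row of the table whenever 5-ALA is suspected.

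**5. What depends on SUSAR status.**
- Dependent: expedited reporting to the MHRA, IMB, RECs and Sponsor (14.3, and the CTRU duties in 14.5), and notification of investigators (Research Fellow duties in 14.5).
- Not dependent: SAE reporting to the CTRU within 24 hours (14.3), the Chief Investigator's immediate review of related events (14.5), and real-time DMEC review of events suspected to be related to 5-ALA and of SAEs not suspected to be related (17.1 and 18.1).

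**6. Which rule prevails.** The Chief Investigator's determination in 14.5 has no exception for listed events. The list in 14.3 recognises only one way out, the Investigator's view of severity. Neither section refers to the other, so the order of precedence is open.

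**The case against.** The strongest reply is that the site's view of expectedness is only preliminary. Every event judged related goes at once to the Chief Investigator, who determines expectedness afresh and could restore SUSAR status. This is a real mitigation. It does not settle the matter, because 14.3 is worded as a firm rule and the protocol does not say that the later determination overrides it.

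A second reply is that the heading confines the list to surgical events, so the clause merely tells sites that ordinary complications are not SUSARs. If so, the clause is redundant for unrelated events, as the table shows, and the limit still has to be written down. As it stands, nothing in the clause confines it to events judged unrelated.

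Several stronger readings are tempting and are not supported:

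- A reader might infer that serious 5-ALA reactions in general are exempt. Only listed events of expected severity are. Photosensitivity, liver enzyme or bilirubin rises, hypotension and brain oedema are not on the list, and many entries are mechanical or local.
- A reader might infer that safety signals would be delayed within the trial. The 24-hour reporting, the Chief Investigator's review and the DMEC's real-time review all continue, and 17.1 and 18.1 set rates that prompt investigation.
- A reader might take arrhythmia as the clearest example. It is a weak one, because tachycardia is a named 5-ALA effect and the product information is not shown.
- A reader might add that 5-ALA is new in this disease. Section 6.4 claims novelty only for combining it with dye mapping, and cites earlier oral use in colorectal tumours. The second cohort may also receive a lower dose rather than a higher one.
- A reader might expect the fix to recover reactions mistaken for complications. It acts only once 5-ALA is suspected. Misattribution of cause is a separate problem.

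**Conclusion.** The point stands in a limited form. The exemption in 14.3 conflicts with 14.1, with the operational rule earlier in 14.3, and with 14.5. Its only practical effect is on suspected 5-ALA reactions that are listed, of expected severity and not covered by the product information. For those, expedited external reporting and investigator notification could be lost; the trial's own oversight is not. The number of such events cannot be estimated, since the documents give no rate for them.

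The three examples rest on one assumption, that the Reference Safety Information does not list acute renal failure, stroke or disseminated intravascular coagulation. Neither it and nor the summary of product characteristics is shown. The conflict itself does not rest on that assumption, because the exemption consults neither document. No endpoint, progression rule or analysis is affected. The change is nevertheless worth making, because the gain is in patient safety and the cost is negligible.

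**What to change.** Reconcile the sections by adding to 14.3, after the exemption clause, text to this effect:

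*This list applies only to events assessed as not related to 5-ALA. For any SAE suspected to be related to 5-ALA, expectedness is judged solely against the Reference Safety Information, whether or not the event is listed. The Chief Investigator's determination of expectedness under section 14.5 applies to listed events as well.*

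Repeat the instruction on the SAE form, where the site records causality and expectedness.

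The cost is a few lines of protocol text, a note on the form, and possibly a few more expedited reports.

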14.5 Responsibilities

Principal Investigator (PI):

- 1 Checking for AEs and ARs when participants attend for treatment / follow-up.
- 2 Using medical judgement in assigning seriousness, causality and preliminary expectedness using the Reference Safety Information approved for the trial.
- 3 Ensuring that all SAEs and SARs (including SUSARs) are recorded and reported to the CTRU within 24 hours of becoming aware of the event and provide further follow-up information as soon as available.
- 4 Ensuring that SAEs and SARs (including SUSARs) are chased with CTRU if a record of receipt is not received within 2 working days of initial reporting.

5 Ensuring that AEs and ARs are recorded and reported to the CTRU in line with the requirements of the protocol.

CTRU

- 1 Provide office hours cover for receipt of all initial and follow up SAEs, SARs, and SUSARs. The CTRU will conduct an initial review of the core dataset prior to forwarding to CI/Research Fellow for medical review.
- 2 Expedited reporting of SUSARs to the relevant Competent Authorities (MHRA and Irish Medicines Board [IMB]), Main RECs in UK and Ireland and Sponsor within required timelines.
- 3 Pass all data to the Research Fellow for databasing.

SJUH Research Fellow:

- 1 Central data collection and verification of AEs, ARs, SAEs, SARs and SUSARs according to the trial protocol onto a database.
- 2 Preparing annual progress reports to Main RECs in UK and Ireland and periodic safety reports to TSC and DMEC as appropriate.
- 3 Reporting safety information to the independent oversight committees identified for the trial (Data Monitoring & Ethics Committee (DMEC) and / or Trial Steering Committee (TSC)) according to the Trial Monitoring Plan.
- 4 Preparing standard tables and other relevant information for the DSUR in collaboration with the CI and ensuring timely submission to the MHRA, IMB and Main REC in UK and Ireland.
- 5 Notifying Investigators of SUSARs that occur within the trial.
- 6 Checking for (annually) and notifying PIs of updates to the Reference Safety Information for the trial.
- 7 Reporting safety information to the CI, delegate or independent clinical reviewer for the ongoing assessment of the risk / benefit according to the Trial Monitoring

Plan.

- 8 Reporting events to collaborating pharmaceutical company in accordance with the trial contract.
- 9 Any duties as delegated by the CI

Chief Investigator (CI) / delegate or independent clinical reviewer:

- 1 Clinical oversight of the safety of patients participating in the trial, including an ongoing review of the risk / benefit.
- 2 Using medical judgement in assigning seriousness, causality and expectedness of SAEs where it has not been possible to obtain local medical assessment.
- 3 Immediate review and determination of expectedness for all events assessed as related to the IMP in the opinion of the local investigator.
- 4 Review of specific SAEs and SARs in accordance with the trial risk assessment and protocol as detailed in the Trial Monitoring Plan.
- 5 Assigning Medical Dictionary for Regulatory Activities (MedDRA) or Body System coding to all SAEs and SARs.
- 6 Preparing the clinical sections and final sign off of the Development Safety Update Report (DSUR).

Trial Steering Committee (TSC):

In accordance with the Trial Terms of Reference for the TSC, periodically reviewing safety data and liaising with the DMEC regarding safety issues.

Data Monitoring & Ethics Committee (DMEC):

In accordance with the Trial Terms of Reference for the DMEC, periodically reviewing unblinded overall safety data to determine patterns and trends of events, or to identify safety issues, which would not be apparent on an individual case basis.

Pharmaceutical company:

- 1 Supply of the Study Drug according to the Drug Transfer Agreement
- 2 Labelling of the Study Drug which with the label provided by the sponsor
- 3 Information of the Principal Investigator on all important new safety information for the Study Drug without delay.
- 4 Information of the Principal Investigator on relevant Quality defects as soon as they are known.

